1. BACKGROUND AND RATIONALE

1.1 Background

Prisons hold some of the most socially disadvantaged people in society (6). Prevalence of neuro-diversities (7), and mental and physical health problems, is higher amongst those living in prison than the general population (6,8,9). Those aged 60 and over are the fastest growing subgroup in prison; there are now three times as many as there were in 2002 (10). Consequently, those residing in the prison are highly likely to have complex social care needs (11). The Care Act 2014 (12) that required local authorities to be responsible for meeting social care needs in prison.

Under the terms of the Care Act and accompanying statutory guidance, from April 2015, local authorities in England have had a legal obligation to assess the need for social care to eligible people in prison and provide it accordingly. Determination of the eligibility of a person's identified needs is a three-stage process. First, it must be shown that the person's needs relate to a physical or mental impairment or illness (as opposed to, for example, their criminal record). Secondly, the adult must be unable to achieve at least two of the ten outcomes set out in the national eligibility criteria as a result of these needs. Thirdly, it must be shown that the inability to achieve these outcomes has a significant impact on the adult's wellbeing. Where a person has needs that do not meet the threshold for eligibility under the Care Act, local authorities must provide information and advice to the individual on how these can be met and prevented from getting worse.

Our previous social care needs prevalence study in men's prisons found that 8 percent of the total sample reported health problems that impacted on daily living; 10 percent of younger prisoners and 21 percent of older prisoners in the total sample reported problems maintaining activities of daily living; and 24 percent of the sample reported that their mental health had an everyday impact on their behaviour (13). Processes to identify and meet these social care needs varied considerably (13,14). There was a lack of active case finding, referral follow-up, and integration between services (13,14). Despite the Care Act, local authority involvement in care remains limited (14). A combination of pressures on local authorities (15) and a lack of active case finding and screening (16) means that few assessments and care packages are delivered, leaving many with presumed unmet care needs (13).

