2. OBJECTIVES AND OUTCOME MEASURES

The aims of WP1 (development work) and WP2 (feasibility RCT and embedded formative process evaluation) are to address the following research questions:

- 1. Can we implement the ET intervention in two men's prisons?
- 2. Is it acceptable and feasible to conduct an RCT to assess whether ET improves the number of met social care needs for adults in prison who are likely to have unmet needs after six weeks and three months, in comparison with care as usual?

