6.1 Recruitment

Participant Identification and Screening

WP1:

The workshops focused on developing the training and supervision manual for ET workers will be advertised through the Association for the Director of Adult Social Services (ADASS), the Health and Justice Research Network at UOM, and social media platforms. The workshops focused on developing the audio, blog, event, film, and webpage content will be promoted through the ADASS Care and Justice Network, the Health and Justice Research Network, the Prison Reform Network, Shaping Our Lives, and social media platforms. Individuals interested in attending the workshops will contact the research team, who will confirm their eligibility before inviting them to take part.

WP2:

For the feasibility RCT, identification of prisoners eligible for participation will occur in two stages. First, the research team will review prisoner lists with prison staff to identify those who meet the following preliminary exclusion and inclusion criteria (see section 5). This group will be weighted with those aged over 50 2:1 to reflect the likely distribution of social care needs in this population. These individuals will be provided with a PIS and Informed Consent Form (ICF) and asked to consent to an interview using the brief ET screening tool (see section 6.2). This tool is aligned with the Care Act and has been adapted from the community for prison settings.

Next, those who consent will complete the brief ET screening tool which asks prisoners whether they (a) consider themselves to have any mental or physical health conditions or impairments or be neurodiverse, and (b) experience difficulties in social care domains such as clothing, food, hygiene, toileting, safety, and family relationships. A series of probing questions relevant to these domains are also asked. The ET screening will be carried out by a researcher to avoid bias from the ET worker developing a relationship and understanding of the needs of participants who later enter the control arm. Those scoring positively on the tool will be eligible for the feasibility trial and will be approached to take part in a further consent process. All participants in the trial will receive an ET screen; this does not, therefore, form part of the intervention, but the acceptability and feasibility of this element will be included in the study.

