7. STUDY INTERVENTION

WP1: no intervention will be administered.

WP2: ET is the treatment that will be administered in the feasibility RCT. It aims to allow the social care needs of prisoners to be met through an integrated, person-centred, trauma-informed intervention. It is a manualised, structured programme that usually includes three core elements of screening, assessment, and social care coordination. In this study, screening will occur before randomisation (Section 6.1), with individuals allocated to the intervention or social care as usual. Assessments will then be conducted with prisoners in the intervention group post-randomisation (Section 6.3), and those with higher-level social care needs will receive social care coordination, whilst those with lower-level social care needs will be given tailored advice and signposting.

Care coordination involves ET workers coproducing care plans with prisoners and/or their carers, family members, or peers. These care plans consider placement in the prison (e.g., adapted cell, healthcare wing, vulnerable prisoner wing) and the support required. All domains of the Care Act are considered, including adaptations to cells and other parts of prisons (e.g., handrails, hygiene equipment, meal trays); coordination of peer support; necessary changes to the regime; support with maintaining personal relationships; and supplementary details of personalised care. The ET workers then coordinate across the complex systems of health, local authority, prison, and third sector organisations to deliver on care plans. A core part of the role of the ET worker is therefore to liaise with health, prison, and local authority staff, making referrals where appropriate, and

aiming to ensure prisoner needs are met (including via improved communication). ET workers act as advocates for the person in prison, including by referring for, feeding into, and attending the Care Act Assessment conducted by the local authority. They also liaise with prison authorities, whose responsibilities include the adaptation of the prison environment for social care.

Signposting to appropriate resources involves providing the participants with tailored advice and information about social care services available to them. These might include (but are not limited to) helplines, healthcare services, or peer support. Information will be developed in consultation with the PPIE panel and individual prisons, and provided in both verbal and written formats.

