9.2 Statistical Analysis Plan

WP1:

The workshops for developing the training and supervision manual for workers will be recorded. The data will be analysed using realist-informed thematic approach (see below for further detail) and, along with information from a prior realist review, used to generate the manual.

WP2:

The feasibility RCT will be reported in accordance with the CONSORT 2010 statement extension to pilot and feasibility trials (59). Descriptive statistics will be reported for feasibility outcomes: numbers screened, eligible, and recruited; retention rates; measure completion rates and data quality; intervention delivery and fidelity (including univariate and bivariate analysis to assess the bespoke fidelity checklist developed in WP1); and attrition during follow-up. The data will inform a potential full RCT, with variability in candidate primary and secondary measures calculated and a sample size (power calculation) for the full RCT estimated for each. Moreover, missing data will be investigated in the feasibility RCT to determine why these are missing and what can be done to minimise missingness in the future full RCT. Simple descriptive analyses will identify the extent of missing data for various questions and questionnaires in the dataset, and models will be fitted to see whether the probability of missingness is linked to baseline characteristics. No statistical comparisons between treatment groups will be undertaken on baseline or follow-up data, as the study is not designed to test effectiveness. Adverse events will be summarised descriptively.

For the cost-effectiveness feasibility analysis, descriptive statistics including data completeness will be reported for each source. The potential cost of ET will be calculated based on information Empowered Together (Coordinated Social Care in Prison)/ET IRAS ID: 361615 Version 1: 01/08/2025

collected using the bespoke fidelity tool about time spent on training, supervision, developing care plans and other components of intervention delivery. Staff time will be costed based on unit costs from the Personal Social Services Resource Unit (60). The team will also investigate the suitability of the ASCOT SCT4, EQ-5D-5L, or ReQoL-10 to calculate the incremental cost per QALY, and the ICECAP-A for YFC gained as part of a full economic evaluation. The extent to which each outcome measure aligns with changes in the CANFOR-R and meeting of social care needs will also be evaluated.

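### The ET screen is a core element of ET but is declared outside the intervention, so its staff time is likely to be missing from the potential cost of ET

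*Protocol*

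**What the plan says.** On what ET is, Section 7 of the protocol states: "It is a manualised, structured programme that usually includes three core elements of screening, assessment, and social care coordination". It then adapts this for the trial: "In this study, screening will occur before randomisation".

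On who screens and how the screen is classed, Section 6.1 states: "The ET screening will be carried out by a researcher to avoid bias from the ET worker developing a relationship". It continues: "All participants in the trial will receive an ET screen; this does not, therefore, form part of the intervention". The same sentence adds that the screen's acceptability and feasibility will still be studied.

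On cost, the potential cost of ET is listed among the WP2 outcomes in Section 2.2. Section 9.2 builds it from what the fidelity tool records about "time spent on training, supervision, developing care plans and other components of intervention delivery", with staff time priced from a published unit-cost source. Screening is not named. Section 2.2 has the fidelity tool completed by a researcher when the three-month intervention ends.

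On fidelity, Section 6.5 says that screening data, together with assessment data, feed the adherence and fidelity checks. The working definition of treatment fidelity in Section 9.1 starts one step later, at the ET assessment.

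**The concern.** The word 'therefore' in Section 6.1 does not follow. A component given to both arms drops out of the difference between them, but it remains part of the package. The protocol's own rationale treats screening as something usual care is short of. Section 1.1 says "a lack of active case finding and screening (16) means that few assessments and care packages are delivered", and Section 1.2 names active case finding and screening tools among the key mechanisms for identifying need.

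The practical consequence is in the costing. If screening is outside the intervention, is done by researchers rather than ET workers, and is absent from the list of costed activities, nobody is instructed to record its time. The cost carried into the budget-impact feasibility work and the full-trial planning would then describe assessment and coordination without the case-finding step that feeds them. Time not logged while recruitment is running is hard to recover afterwards.

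**Working it through.** **Step 1. The passages side by side.**

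- Section 7: screening is a core element of ET.
- Section 6.1: the screen is not part of the intervention, and a researcher does it.
- Section 9.2: the cost of ET is the time spent delivering the intervention, taken from the fidelity tool.
- Section 2.2: the tool is completed at the end of each three-month intervention.
- Section 6.5: screening data enter the fidelity checks, but time is not mentioned, and the screens referred to are those of trial participants.

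No section provides for recording time on screens of people who are not recruited. The omission follows from Sections 6.1 and 9.2 taken together. Neither states it outright.

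**Step 2. The plan's own screening figure.** Section 9.1 expects 40% of those screened to be recruited: 76 / 0.40 = 190 screens. This reproduces the stated 190. So 190 − 76 = 114 screens concern people who are never randomised.

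**Step 3. Screens per screen-positive person.** The protocol gives no screen-positive rate. Assume that 60% of positives are recruited, the figure used as the green threshold in Section 2.2.

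- Positives: 76 / 0.60 ≈ 127
- Screens per positive: s = 190 / 127 ≈ 1.5
- The 114 screens split into 190 − 127 = 63 negatives and 127 − 76 = 51 positives not recruited.

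**Step 4. Share of staff time left out.** With h hours per screen and T hours of ET worker time per participant:

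omitted share = s·h / (s·h + T)

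The protocol gives neither h nor T. Assume h = 0.5 to 1 and vary T, with s = 1.5:

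| T (assumed) | h = 0.5 | h = 1 |
|---|---|---|
| 5 h | 0.75 / 5.75 = 13.0% | 1.5 / 6.5 = 23.1% |
| 10 h | 0.75 / 10.75 = 7.0% | 1.5 / 11.5 = 13.0% |
| 20 h | 0.75 / 20.75 = 3.6% | 1.5 / 21.5 = 7.0% |

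**Step 5. Sensitivity to the 60%.** If a proportion r of positives is recruited, s = (190 / 76) × r = 2.5r. At T = 10 h:

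- r = 0.4, s = 1.0: 0.5 / 10.5 = 4.8% to 1 / 11 = 9.1%
- r = 0.8, s = 2.0: 1 / 11 = 9.1% to 2 / 12 = 16.7%

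The direction is downward for any positive screening time left out. Only the size depends on the assumptions.

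**The case against.** The best defence of the plan has three parts.

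**The adaptation is disclosed.** Section 7 says that ET "usually includes three core elements of screening, assessment, and social care coordination", and at once explains that here screening comes before randomisation. The trial summary describes ET through systematic assessment and coordination. This shows that nothing is hidden. It does not settle whether the cost of ET should include the screen.

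**The cost exclusion is not stated.** The Section 9.2 list ends in an open category, the fidelity tool is still to be developed, and Section 6.5 brings screening data into the fidelity checks. A reader might infer that screening is expressly excluded from the cost. The documents do not go that far. Even so, an open category of intervention components does not readily take in something Section 6.1 says is not one, and Section 6.5 says nothing about time or about people who are not recruited.

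**The comparator is legitimate.** A reader might infer that the control arm is no longer care as usual, and that a definitive trial would lose power because controls gain from being screened. The documents do not support this. Research question 2 concerns "adults in prison who are likely to have unmet needs after six weeks and three months, in comparison with care as usual". A positive screen is the inclusion criterion that identifies those people, and controls then receive social care as usual. Section 10.2 has eligibility entered in health records, which could reveal that a screen was positive, but no section passes a control participant's screening findings to care providers. Nothing in the protocol gives an effect of screening alone, and Section 9.2 rules out between-arm comparisons in this study. The comparator point is one of wording only.

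A reader might also size the omission from screens per recruit (190 / 76 = 2.5). That would charge ET for positives who were not recruited into the trial, which is a cost of the research. Screens per positive is the right basis.

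**Conclusion.** The point stands for the costing. As written, the plan classes a core element of ET as outside the intervention and gives no instruction to record its time, so the potential cost of ET is likely to be too low for a prison that adopts the full package. This rests on reading Sections 6.1 and 9.2 together, with Section 6.5 unreconciled.

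The size cannot be fixed from the protocol. Under the central assumptions (0.5 to 1 hour per screen, 10 ET worker hours, 60% of positives recruited) it is about 7% to 13% of staff time. Varying ET worker hours from 5 to 20 gives about 4% to 23%.

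The screen's place before randomisation is sound, and the point affects no sample size or progression criterion.

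**What to change.** 1. **Section 6.1.** Replace the statement that the screen is not part of the intervention. Say instead that it is an element of ET delivered to both arms before randomisation, so it lies outside the randomised contrast but inside the ET package. Describe the comparator as social care as usual following a positive ET screen. This is a clarification and changes no procedure. Align Sections 6.5 and 7 with it.

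2. **Section 9.2.** Record the time taken for each ET screen on the existing screening form, for everyone screened. Cost it per screen-positive person as time per screen × number screened / number screen-positive, using the same unit-cost source. Report the potential cost of ET with and without screening.

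The cost is one extra data field, one more line in a descriptive table, and a slightly higher reported cost of ET. No participants, visits or staff are added, but the field must be in place before screening starts.

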6.2 Consent

Consent for participation in WP1 and WP2 will be sought by a member of the research team, who will act in accordance with the ethically approved protocol, principles of Good Clinical Practice (GCP), and Declaration of Helsinki. All people authorised to take consent will be recorded in the delegation log.

WP1:

Individuals expressing an interest in attending the workshops for developing the manual for ET workers will be provided with an ICF and PIS. These documents will be produced in collaboration with experts-by-experience. Communication and literacy issues will be taken into consideration, and researchers will read the documents aloud to expert-by-experience participants to minimise embarrassment, unless prompted not to. After receiving the ICF and PIS, individuals will be given at least 24 hours to decide whether they want to take part in the workshops. If they have questions about the consent process or the study, they will be able to contact the research team

using an email address provided in the PIS. If an individual does decide to take part, they will be asked to complete the ICF prior to the workshop and email it to a member of the research team (or ask someone else to email it on their behalf).

WP2:

Feasibility RCT

For the feasibility RCT, the preliminary eligibility screen (using the prison lists) will be conducted without prior consent. Individuals who are eligible to participate will be provided with an ICF and PIS by a member of the research team to help them to understand the study. The PIS will explain to participants that they are able to decline or withdraw from the study without giving a reason and without prejudice to future care. It will also outline the limits of confidentiality, making it clear that this will be broken if participants disclose that they intend to harm themselves or others, or share information that researchers in prison settings are obligated to report (see section 1.5). Given that prisoners often have lower literacy levels and higher rates of cognitive impairment than people in the community, the ICF and PIS will be designed in an easy-to-read format that is produced in collaboration with experts-by-experience. In addition, the research team will read the documents aloud to potential participants to minimise embarrassment, unless prompted not to. Potential participants will be given adequate time to consider if they want to take part, and will be given an opportunity to discuss the study with a member of the research team before making a decision.

If concerns about capacity to consent arise, a senior member of the research team will conduct a review, and an opinion will be sought from healthcare staff where required. The research team will receive training on the principles of the Mental Capacity Act and its Code of Practice (54) and GMC guidance will be followed (55). Where prisoners do have capacity, audio or written informed consent will be sought. The consent process will be completed in a face-to-face meeting between the potential participant and the researcher. In this meeting, the researcher will work through the ICF and ask if the participant has any questions. Participants who consent to involvement will complete two separate ICFs, with one held by the research team and one retained by the participant. If an individual lacks capacity but indicates a wish to take part in the study, the research team will attempt to identify a 'personal consultee' as defined by the Mental Capacity Act to receive study information and advise on participation. In cases where this is not possible, we will seek advice from a nominated (professional) consultee in the prison. We will discuss the study with the person themselves in a way appropriate to their understanding, take account of their expressed wishes, and not include them in research if they do not assent. For participants recruited in this way, no actions will be taken during any part of the study if the participant appears to object (unless these are vital to protect them from harm), researchers will consider the interests of the participant above all else, and the person will be withdrawn if they give any indication that they do not want to take part. Capacity will be assessed at each contact and monitored in an ongoing manner for all participants. The ICF will include an option to indicate a preference 'for' or 'against' continued participation should an individual lose capacity during the study. Similarly, if an individual regains capacity during the study, they will be reconsented.

This process will be followed for the initial ET screening and the full feasibility RCT. We will ask participants to provide a variety of contact details in case they are released or transferred. We will consult with our PPIE groups about acceptable information to ask for, however this is likely to include friends and family members, and community probation workers. Consent to contact Empowered Together (Coordinated Social Care in Prison)/ET IRAS ID: 361615 Version 1: 01/08/2025

participants in the community and/or through the National Probation Service in the event that they are released or transferred will also be sought at this stage.

Embedded Formative Process Evaluation

Prisoners participating in the embedded formative process evaluation will be given an additional ICF and PIS for the interviews, as well as for the observations (for those selected for the case studies), by a member of the research team. PISs will explain to participants that they are able to decline or withdraw from this element of the study without giving a reason and without prejudice to future care. These will also outline the limits of confidentiality, making it clear that this will be broken if participants disclose that they intend to harm themselves or others, or share information that researchers in prison settings are obligated to report including risk to the safety of themselves and others. As prisoners often have lower literacy levels and higher rates of cognitive impairment than people in the community, the ICFs and PISs will be designed in an easy-to-read format produced in collaboration with experts-by-experience. The researchers will also read the ICFs and PISs to potential participants to minimise embarrassment, unless prompted not to. Potential participants will be given adequate time to consider if they want to take part and will be provided with an opportunity to discuss with a member of the research team before making a decision. Concerns about capacity will be addressed in the same way as in the feasibility RCT.

Staff participating in the process evaluation will similarly be provided with an ICF and PIS, which explain that they are able to decline or withdraw from the study without giving a reason. After receiving the ICF and PIS, individuals will be given at least 24 hours to decide whether or not they want to take part in the workshops. If they have questions about the consent process or the study, they will be able to contact the research team using an email address provided in the PIS. If an individual does decide to take part, they will be asked to complete the ICF prior to interview, and email it back to a member of the research team.

